APPENDIX A (CONT'D)

Table 3 Schedule of eDiary and Actigraphy Assessments

eDiary and actigraphy devices are provided to subjects at the screening visit. eDiary devices are collected at the Follow-up Visit. Actigraphy watches will be returned to site and new watches dispensed to subject as needed during the study period.

Device	Assessment	Frequency and Duration of Assessment
eDiary	WI-NRS	Once daily from Screening visit through the Follow-up visit
eDiary	AI-NRS	Once daily from Screening visit through the Follow-up visit
eDiary	ItchyQOL	Once at screening, baseline*, Week 2, Week 4, Week 6, ETD, and Follow-up visit
eDiary	sPGA	Once at screening, baseline*, Week 2, Week 4, Week 6, ETD, and Follow-up visit
eDiary	PGIC	Once at Week 2, Week 4, Week 6, ETD, and Follow-up visit
Actigraphy watch	Scratching	Continuous nighttime monitoring from Screening visit through the Follow-up visit
Actigraphy watch	Sleep	Continuous nighttime monitoring from Screening visit through the Follow-up visit

*Baseline assessments need to be done prior to initial study drug administration.

APPENDIX B LIST OF STRONG CYP3A4 INHIBITORS

The list of strong CYP3A4 inhibitors is based on the FDA list effective September 26, 2016, *Examples of clinical inhibitors for P450-mediated metabolisms (for concomitant use clinical DDI studies and/or drug labeling)*³⁸:

1. boceprevir
2. clarithromycin
3. cobicistat
4. conivaptan
5. danoprevir and ritonavir
6. diltiazem
7. elvitegravir and ritonavir
8. regular grapefruit juice consumption
9. idelalisib
10. indinavir and ritonavir
11. itraconazole^a
12. ketoconazole^a
13. lopinavir and ritonavir
14. nefazodone
15. nelfinavir
16. paritaprevir and ritonavir and (ombitasvir and/or dasabuvir)
17. posaconazole^a
18. ritonavir
19. saquinavir and ritonavir
20. telaprevir
21. tipranavir and ritonavir
22. troleandomycin
23. voriconazole^a

^a Topical formulations of azoles are not considered strong CYP3A4 inhibitors due to limited systemic absorption.

1 STUDY DESCRIPTION

1.1 Introduction

In this study serlopitant is being studied for the treatment of pruritus (itching) in adults and adolescents with a history of atopic dermatitis. Atopic dermatitis (AD) is an inflammatory, chronically relapsing and intensely pruritic skin disease referred to as “the itch that rashes.” Pruritus is the “cardinal symptom” in AD ([Lewis-Jones 2006](#)).

Serlopitant is a small molecule, highly selective neurokinin-1 receptor (NK₁-R) antagonist that is administered orally. NK₁-R stimulation has been shown to be an important pathway for pruritus perception ([Ständer 2015](#)). Evidence suggests that inhibition of this pathway results in decreased pruritus, see protocol for details. Prior to initiation of this study, serlopitant was evaluated in over 1,000 subjects across thirteen Phase 1 studies and four Phase 2 studies.

1.2 Objectives

Study MTI-103 contains primary and secondary objectives.

The primary objective is to assess the efficacy of serlopitant for the treatment of pruritus in adults and adolescents with a history of atopic dermatitis.

The secondary objectives of this study are as follows:

- To assess the safety and tolerability of repeated oral doses of serlopitant in adults and adolescents with a history of atopic dermatitis
- To assess the psychometric properties of Worst-Itch Numeric Rating Scale (WI-NRS)

1.3 Study Design

This is a double-blind, randomized, placebo-controlled study. Approximately 450 subjects will be randomized in a 1:1:1 ratio to receive daily oral doses of serlopitant 1 mg, 5 mg, or placebo for 6 weeks. The study will consist of three periods (screening, treatment, follow-up), for a total study period of approximately 12 weeks.

During the screening period, subjects will be provided with an electronic device for recording electronic diary (eDiary) assessments throughout the study. This eDiary will be used to capture efficacy endpoint data and treatment information (see [Table 1](#)). At the Baseline visit, eligible subjects will be randomized, and study drug dispensed beginning with a loading dose of 3 tablets to be taken at bedtime that same day (Study Day 1). Starting on Study Day 2, subjects will take one tablet per day at bedtime. Treatment will continue for 6 weeks. The primary efficacy endpoint will be assessed during Week 6.

After completion of the 6-week treatment period, all subjects will enter a 4-week follow-up period. Subjects who discontinue treatment early at any time during the treatment period will

have an Early Treatment Discontinuation (ETD) visit within 7 days after their last dose of study drug in addition to a follow-up visit 4 weeks after the end of treatment or at Week 6, whichever is later.

An abbreviated schedule of activities for the study can be found in [Table 2](#) with greater details available in the protocol.

Table 1 Schedule of eDiary and Actigraphy Assessments

Device	Assessment	Timing of Assessments
eDiary	WI-NRS / AI-NRS	Once daily for duration of the study
	ItchyQoL / sPGA	At Screening, Baseline visit, Days 15 (± 2), 29 (± 3), 43 (± 3) and 28 days (± 3) after the ETD visit
	PGIC	Days 15 (± 2), 29 (± 3), 43 (± 3) and 28 days (± 3) after ETD visit
Actigraphy watch	Scratching / Sleep	Nighttime monitor for duration of the study

Table 2 Schedule of Visit Activities

Examination	Screening	Baseline Day 1	Week 1 Day 8	Week 2 Day 15	Week 4 Day 29	Week 6 Day 43 / ETD	Follow-up ETD + 28
Informed consent	X						
Medical history	X						
I/E criteria	X	X					
Randomization		X					
Physical exam	X			X		X	X
Vital signs	X	X		X	X	X	X
ECG	X			X			X
Labs	X			X		X	X
PK				X	X	X	
IGA-AD	X	X		X	X	X	X
5-D Pruritus Scale	X	X		X	X	X	X
Concomitant medications Procedures/ Non-Medication Therapy		X	X	X	X	X	X
Adverse events		X	X	X	X	X	X

1.4 Method of Assigning Subjects to Treatment Groups

Subjects will be randomized to serlopitant 1 mg, 5 mg, or placebo in a 1:1:1 ratio. Stratified permuted block randomization will be used. Randomization will be stratified by sex (male, female) and race (white, non-white). An Interactive Web Response System will be used to perform the randomization.

1.5 Treatment Blinding

This is a double-blind study. The sponsor will not have access to unblinded data during the study and there is no expectation that the study data (e.g. adverse events, dosing, or lab results) will unblind the sponsor, investigator or subjects. Greater details concerning study blinding can be found in a separate blinding plan.

1.6 Decision Rule and Sample Size

The significance level for this study is 5% (one-sided). If the one-sided p-values are less than 5% then the null hypothesis of no treatment effect is rejected. If the one-sided p-values are additionally less than 2.5%, then the serlopitant-based regimen will have met the generally accepted level of evidence required to demonstrate efficacy.

This study contains two active dosing arms. A stepdown procedure will be used to control for multiplicity. This procedure will start by testing the primary endpoint for the 5 mg treatment group and then proceed to the 1 mg group should statistical significance (one-sided p-values < 0.05) be reached for the 5 mg vs placebo comparison.

Statistical significance for the key secondary endpoints will be dependent upon statistical significance being reached for the primary endpoint at the given dose level (i.e. a gatekeeper within dose arm will be used for the secondary endpoints). As there are multiple secondary endpoints a stepdown procedure will be used starting with the WI-NRS 4 point responder rate endpoint, then the ItchyQoL.

The target sample size of 450 randomized and dosed subjects (150 per group) has been determined based upon a 1:1:1 allocation of subjects to treatment groups, an assumed common treatment effect for the 1 mg and 5 mg arms, and a 5% one-sided alpha level. One-hundred and fifty subjects per group results in 90% power for each test individually assuming a treatment effect (placebo change from baseline - serlopitant change from baseline) of -1 and a standard deviation of 2.9.

The sample size calculations have been performed in PASS 13 using a t-test. The primary analysis will control for the stratification factors. It is expected that this unstratified power estimate will under-estimate the true power as it does not take the variance reduction resulting from stratification into account ([Matts and Lachin 1988](#)).

2 STATISTICAL METHODS

2.1 Populations Analyzed

Four analysis populations will be defined. These populations are:

- Screened Population – All subjects who provide informed consent and attend the screening visit.
- Randomized Population – All subjects who are randomized. Subjects will be analyzed within the treatment group to which they are randomized.
- Full Analysis Set (FAS) – Subset of subjects in the randomized population who received at least one dose of study medication. Subjects will be analyzed within the treatment group to which they are randomized.
- Safety Population – Subset of subjects who received at least one dose of study medication. This population will be analyzed based upon the actual treatment received. If a dosing error occurs and the subjects received treatment at more than one dose level, where placebo is considered a dose level, they will be summarized in the dose group which represents the highest dose received.

2.2 Study Drug Dosing and Compliance

Study drug usage (medication taken yes/no) on each study day will be recorded within the eDiary. Tablet counts will also be recorded in the case report form. Each data source will be independently used to summarize tablets used and compliance. In this way two measures of dosing and compliance will be available. The calculation of these two measures will be identical and hence any difference between them will be reflective of the extent the subject reported dosing data in the eDiary and tablet counts disagree.

The total number of tablets used will be summarized along with the duration of treatment and compliance. The duration of treatment (last dose date – first dose date + 1) will be based on dosing information provided within the CRF. Compliance will be calculated as,

$$\text{Compliance}(\%) = \frac{\text{Tablets Used}}{\text{Last Dose Date} - \text{First Dose Date} + 3}$$

The number of tablets used will be based upon the results provided within the eDiary and the recorded tablet counts within eDC. Should a subject not return a bottle, for compliance calculations it will be assumed they returned the average number of tablets that were returned in their other bottles. Subjects with no returned bottles will have missing tablet count compliance. The denominator for the compliance calculation includes a + 3 to account for the loading dose received on Study Day 1. This compliance calculation implies a subject who takes treatment for one week but takes all expected tablets for that week will be 100% compliant with treatment.

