5 STUDY DRUG

5.1 Study Drug Supply, Route of Administration, and Storage

The study drug in this study is serlopitant 1 mg, serlopitant 5 mg, or placebo, in a film-coated tablet formulation for oral administration. The serlopitant tablets contain microcrystalline cellulose, mannitol, croscarmellose sodium, silicon dioxide, sodium lauryl sulfate, and magnesium stearate, and are film coated with Opadry™ Brown. The placebo tablets contain microcrystalline cellulose, lactose monohydrate, and magnesium stearate, and are film coated with Opadry™ Brown.

The study drug will be provided in bottles that can be stored at room temperature (59-86°F).

The tablets will be supplied in bottles, with 18 tablets per bottle. One bottle will be issued via Interactive Web Response System (IWRS) at baseline and at the Week 2 and Week 4 visits, for a total of 3 bottles dispensed for subjects completing 6 weeks of study drug treatment.

Additional details regarding study drug supplies can be found in the Pharmacy Manual.

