5.3 Dosing Regimen

Subjects will take a loading dose (3 tablets taken orally) at bedtime on the first day of the treatment period (Study Day 1). Starting on Study Day 2, subjects will take one tablet per day taken orally at bedtime. Subjects will be instructed to take all doses at approximately the same time each day and no sooner than 2 hours before or after a meal.

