6.5.1 Informed Consent/Assent

Informed consent will occur prior to any protocol-mandated procedures, including the stopping of any excluded therapies. This may occur prior to the initial Screening visit.

6.5.2 *Screening Visit/Period*

An initial Screening visit should be scheduled to occur 14 days (-2 days, +3 days) prior to the Baseline visit. The following screening procedures are to be performed at the initial Screening visit:

- Inclusion/exclusion criteria review
- Medical history
- Complete physical examination
- Vital signs (including height and weight)
- IGA-AD
- 5-D Pruritus Scale
- ECG
- Schedule the baseline visit
- Provide actigraphy device with instructions
- Provide eDiary with instructions

During the screening period (after consent/assent and prior to the baseline visit), the following screening procedure is to be performed:

- Laboratory
 - Reproductive endocrine labs for females
 - Urine pregnancy test for females of childbearing potential (with positive or equivocal results confirmed by a serum pregnancy test)
 - Endocrine and cardiac
 - Hematology
 - Chemistry
 - Urinalysis

6.5.3 *Baseline Visit*

The Baseline visit occurs 14 days (-2 days, +3 days) after the Screening visit. At the Baseline visit, the following procedures and assessments are to be performed:

- Inclusion/exclusion criteria review
- Vital signs

- IGA-AD
- 5-D Pruritus Scale
- Concomitant medications
- AEs
- Randomization if eligible
- Dispense study drug
- Schedule future visits

Randomized subjects will begin treatment with study drug in the evening of the Baseline visit (Study Day 1).

6.5.4 *Week 1 Visit*

The Week 1 visit is a telephone visit that occurs 7 days (± 3 days) after the Baseline visit (Study Day 5-11). At the Week 1 visit, the following procedures and assessments are to be performed:

- Concomitant medications
- AEs

6.5.5 *Week 2 Visit*

The Week 2 visit occurs 14 days (± 2 days) after the Baseline visit (Study Day 13-17). At the Week 2 visit, the following procedures and assessments are to be performed:

- Vital signs (including weight)
- IGA-AD
- 5-D Pruritus Scale
- Targeted physical examination
- ECG
- Laboratory
 - Urine pregnancy test for females of childbearing potential (with positive or equivocal results confirmed by a serum pregnancy test)
 - Hematology

- Chemistry
- Urinalysis
- PK blood sample collection
- Concomitant medications
- AEs
- Collect returned study drug
- Dispense study drug

6.5.6 *Week 4 Visit*

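### SAP 2.2's rule for an unreturned bottle ignores how long that bottle was in use, so an early stopper's tablet-count compliance can come out far too high or far too low

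*SAP*

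**What the plan says.** SAP 2.2 defines two compliance measures, one from the eDiary and one from tablet counts. Both are tablets used divided by (last dose date − first dose date + 3). On the constant it says: "The denominator for the compliance calculation includes a + 3 to account for the loading dose received on Study Day 1".

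When a bottle does not come back, for compliance calculations "it will be assumed they returned the average number of tablets that were returned in their other bottles". A subject who returns no bottle at all has missing tablet-count compliance.

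The section makes two statements about how the result behaves:

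- "This compliance calculation implies a subject who takes treatment for one week but takes all expected tablets for that week will be 100% compliant".
- The two measures are calculated in the same way, so a difference between them shows how far diary and tablet counts disagree.

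Protocol 5.1 gives the supply: "The tablets will be supplied in bottles, with 18 tablets per bottle", issued "at baseline and at the Week 2 and Week 4 visits, for a total of 3 bottles dispensed". Protocol 5.3 gives the regimen: "Subjects will take a loading dose (3 tablets taken orally) at bedtime on the first day of the treatment period", and then "Starting on Study Day 2, subjects will take one tablet per day taken orally at bedtime".

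**The concern.** Borrowing the average from the other bottles is reasonable only if the missing bottle was in use for about as long as they were. That is roughly so for a completer. It is not so for a subject who stops a day or two into a new bottle: the borrowed figure describes about 14 days of dosing, while the denominator stops at the last dose.

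Three things are at stake, all within the descriptive reporting of exposure:

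- A subject who missed no dose can be reported at well over 100%, which looks like overdosing, or at a small fraction of 100%, which looks like gross non-adherence.
- Real non-adherence before withdrawal can be hidden.
- A gap between the two measures no longer means what SAP 2.2 says it means. It can arise from the imputation alone, when diary and tablet counts agree perfectly.

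**Working it through.** **Inputs**

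- 18 tablets per bottle; one bottle at each of baseline, Week 2 and Week 4 (Protocol 5.1).
- 3 tablets on Day 1, then 1 daily at bedtime (Protocol 5.3).
- Week 2 visit at Day 15, window Day 13 to 17 (Protocol 6.5.5); Week 4 visit at Day 29 (Protocol Appendix A, Table 2).
- With first dose on Day 1 and last dose on Day L, the denominator is L − 1 + 3 = L + 2 (SAP 2.2).
- Credited use of an unreturned bottle = 18 − mean number returned in the subject's other bottles (SAP 2.2).
- Assumption: the bedtime dose on a visit day comes from the newly dispensed bottle.

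**The SAP's own figure.** One week, all doses taken: (3 + 6)/(7 − 1 + 3) = 9/9 = 100%. It reproduces.

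**Bottle 1 returned, bottle 2 not returned, no missed doses.** By the Day 15 visit the subject has used 3 + 13 = 16 tablets and returns 2. The rule assumes 2 left in bottle 2, so it credits 18 − 2 = 16. Total credited: 16 + 16 = 32, whatever the last dose day.

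| Last dose day | True use | Denominator | Credited use | Tablet-count compliance |
|---|---|---|---|---|
| 14 (none from bottle 2) | 16 | 16 | 32 | 200% |
| 15 | 17 | 17 | 32 | 188.2% |
| 16 | 18 | 18 | 32 | 177.8% |
| 21 | 23 | 23 | 32 | 139.1% |
| 28 | 30 | 30 | 32 | 106.7% |

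Moving the Week 2 visit across Day 13 to 17 changes little: 200% with no dose from bottle 2, 186.7% to 189.5% with one, 175.0% to 180.0% with two.

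**Bottles 1 and 2 returned, bottle 3 not returned.** Use is 16 and 14, returns are 2 and 4, mean 3. Credited use of bottle 3 is 15, total 16 + 14 + 15 = 45. Last dose Day 28: 45/30 = 150%. Day 30: 45/32 = 140.6%.

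**Bottle 1 not returned, bottle 2 returned after an early stop.** The short second bottle is now projected onto the full first one. Last dose Day 16: bottle 2 use is 2, so 16 come back; bottle 1 is credited with 18 − 16 = 2; (2 + 2)/18 = 22.2%. Last dose Day 21: (7 + 7)/23 = 60.9%.

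**Completers, last dose Day 42.** Expected use is 16 + 14 + 14 = 44 and the denominator is 42 + 2 = 44. Bottle 1 missing: 14 + 14 + 14 = 42, 42/44 = 95.5%. Bottle 2 or bottle 3 missing: 16 + 14 + 15 = 45, 45/44 = 102.3%.

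**Masked non-adherence.** A subject takes 8 of the 16 tablets expected from bottle 1 (10 returned), has a last dose on Day 16 and does not return bottle 2. The rule credits 8 more: 16/18 = 89%. True use is at most 8 + 2 = 10, or 10/18 = 56%.

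**Comparison with the diary.** For the fully adherent subject with last dose Day 16, an accurate diary gives (3 + 15)/18 = 100%. The tablet count gives 178% or 22%, depending only on which bottle is missing.

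**The case against.** The strongest reply is that this is an edge case in a summary on which nothing depends. SAP 2.1 defines the Full Analysis Set and the Safety Population by receipt of at least one dose, there is no per-protocol set, and compliance enters no efficacy test. Protocol 8.7 bases compliance and exposure summaries on the eDiary; the tablet count is an addition in the SAP. Protocol 5.9 asks for all partly used and empty bottles back at each visit, and Protocol 6.5.8 has study drug collected at the early discontinuation visit. A value of 178% would also stand out next to a diary value of 100%. All of this stands, and it keeps the point small. It does not make the reported number right: Protocol 5.6.1 foresees loss to follow-up and withdrawal of consent, and the SAP has a rule for unreturned bottles because it expects some.

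A reader might also infer more than the documents support:

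- **That the one-week statement is contradicted.** It is not, literally. A second bottle is issued no earlier than Day 13, so a one-week subject has a single bottle: returned, it gives 100%; not returned, the measure is missing. What fails is the extension of that principle to subjects who have received a second bottle.
- **That compliance is biased upward overall.** The direction depends on which bottle is missing, and subjects who return nothing are set to missing. The documents give no non-return rates.
- **That the arms are affected differently.** This would need non-return and early stopping to differ by arm, and nothing in the documents shows that they will.
- **That total tablets used is inflated.** The rule is worded for compliance calculations. SAP 3.3.5 bases tablets used on counts reported in the CRF, and neither section says whether the imputed count enters that total. This is a gap to close, not a demonstrated error.

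A restriction to returned bottles has a price too: the two measures then cover different time spans for these subjects, although SAP 2.2 wants them calculated identically.

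**Conclusion.** The point holds as a minor one. For a subject who stops early with one bottle unreturned and another returned, the rule in SAP 2.2 can give a badly wrong tablet-count compliance in either direction. In the worked case, with no missed doses, the values are 178% or 22% at last dose Day 16. The 178% is an example and not a ceiling: 188% follows if one dose came from bottle 2 and 200% if none did. For completers the error is within about 5 percentage points. SAP 2.2's reading of a difference between the two measures as disagreement between sources fails for these subjects.

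The effect on an arm mean is probably modest. If 1 to 5 of 150 subjects in an arm scored 178% in place of 100% (an assumed range, since the documents give none), the mean would move by 78/150 = 0.5 to 5 × 78/150 = 2.6 percentage points. Individual listings and the reported maximum or minimum would be affected more visibly.

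The arithmetic rests on the visit-day dose coming from the new bottle and on visits at the target days; varying the Week 2 visit across its window does not change the conclusion. No efficacy analysis, analysis population or eDiary result is touched.

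**What to change.** Change SAP 2.2, for tablet-count compliance only:

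- For a subject with an unreturned bottle, use only the dispensing intervals of the returned bottles, in both numerator and denominator. An interval runs from the day a bottle is dispensed to the day before the next one is dispensed, or to the last dose date if that comes first.
- Add the two extra loading-dose tablets to the denominator only when bottle 1 is among the returned bottles.
- State that imputed counts do not enter the summary of total tablets used.
- Report the number of subjects with unreturned bottles by arm.

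Check on the worked cases with last dose Day 16: bottle 2 missing gives 16/(14 + 2) = 100%; bottle 1 missing gives 2/2 = 100%. With all bottles returned the formula is unchanged (44/44 for a completer). A missing middle bottle needs no separate rule, because its interval drops out.

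The cost is a short addition to the SAP and some programming with bottle-level dispensing and return dates. The downside is that for these subjects the tablet-count measure covers a shorter period than the eDiary measure. A table footnote should say so, and the eDiary remains the source for the uncovered days.
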